DMC	Data Monitoring Committee
DSPC	1, 2-distearoyl-sn-glycero-3-phosphocholine
eGFR	estimated Glomerular Filtration Rate
ENR	Enrolled Set
FAS	Full Analysis Set
FEF ₂₅₋₇₅	Forced Expiratory Flow at 25-75%
FEV ₁	Forced Expiratory Volume at 1 Second
FVC	Forced Vital Capacity
eCRF	electronic Case Report Form
ISC	Independent Study Coordinators
IRT	Interactive Response Technology
MedDRA	Medical Dictionary for Drug Regulatory Affairs
MIC	Minimum Inhibitory Concentration
o.d.	once a day
PCR	Protein-creatinine ratio
	
	
PK	Pharmacokinetics
PKAS	Pharmacokinetic Analysis Set
PKSSAS	Pharmacokinetic Sub-Study Analysis Set
PPS	Per-Protocol Set
PRO	Patient Reported Outcomes
PSD	Premature Subject/Patient Discontinuation
PT	Preferred Term
QoL	Quality of Life
QOL-B	Quality of Life Questionnaire for Bronchiectasis
RAN	Randomized population
SAF	Safety Set
SAP	Statistical Analysis Plan
SOC	System Organ Class

█
TBL

█
Total Bilirubin

TD

Study Treatment Discontinuation

TIP

Tobramycin inhalation powder

TFLs

Tables, Figures, Listings

ULN

Upper Limit of Normal

WHO

World Health Organization

1 Introduction

This statistical analysis plan (SAP) is based on the amended protocol version 02 dated 09th February 2018, and the business decision to close the trial earlier than planned (but not due to safety or efficacy reasons) by the Novartis. Recruitment has been stopped on 02nd October 2018 with 107 patients randomized as against 180 patients initially planned. With this premature closure and reduced sample size, the inferential analysis, regardless if it's pre-defined, can be considered as exploratory, the results obtained should be interpreted with the caution. The plan provides a technical and detailed elaboration of the statistical analyses of the efficacy, safety and tolerability of different doses of tobramycin inhalation powder (TIP) in patients with Non-Cystic Fibrosis Bronchiectasis and pulmonary *P. aeruginosa* infection. The specifications for tables, figures, and listings (TFLs) will be included in a separate document.

A clinical study report (CSR) will be written based on the results of the statistical analyses planned within this SAP. Results will also be used for the various publications.

1.1 Study design

This is a blinded, randomized, dose and regimen finding trial utilizing a 3 treatment cohort design where active TIP, TIP/Placebo cyclical, or placebo in addition to the local standard care within each cohort are delivered once or twice daily (Figure 1). The study will implement a within-cohort blinding approach. This allows assessment of the tolerability (defined as the rate of local AEs) of different doses and regimens of TIP, and also saves the treatment burden that would be imposed for blinding across all arms. Note that all of the patients in the study would need to inhale the maximal dose of 10 capsules every day (5 morning + 5 evening) to maintain the blind between cohorts (different dose levels) and within a cohort (different regimens).

Approximately 180 eligible patients will be randomized to 1 out of the 3 cohorts in a ratio of 1:1:1. The patients within each cohort will be randomized to blinded TIP or placebo with the following randomization scheme: TIP: TIP/placebo cyclical: placebo, in a 2:2:1 ratio.

At Visit 101 (see protocol [Table 6-1 – Assessment schedule]), all eligible patients will be randomized via Interactive Response Technology (IRT) to 1 of the treatment arms with the randomization strata (use of macrolides as part of their standard of care therapy yes/no). To evaluate serum pharmacokinetics (PK) in approximately 16 patients on active treatment, at least 20-22 patients from each cohort (at least 60 total patients) will participate in a PK sub-study. To ensure a balanced distribution across cohorts, this will be captured in IRT. The investigator or his/her delegate will contact the IRT after confirming that the patient fulfills all the inclusion/exclusion criteria. The IRT will assign a randomization number to the patient, which will be used to link the patient to a treatment arm and will specify a unique medication number for the first package of investigational treatment to be dispensed to the patient. The randomization number will not be communicated to the user.

The randomization numbers will be generated using the following procedure to ensure that treatment assignment is unbiased and concealed from patients and investigator staff. A patient randomization list will be produced by the IRT provider using a validated system that automates the random assignment of patient numbers to randomization numbers. These randomization numbers are linked to the different treatment arms, which in turn are linked to medication numbers. A separate medication list will be produced by or under the responsibility of Novartis Drug Supply Management using a validated system that automates the random assignment of medication numbers to packs containing the investigational drug(s).

The treatment arms distributed among the 3 cohorts are described below. TIP is supplied in hard capsules at 28mg dosage strength, therefore 3 cohorts correspond to 3 different dose

levels of TIP, i.e., 84mg once a day (o.d.), 140mg o.d. and 112mg twice a day (b.i.d.).

Cohort A: 3 capsules o.d.

- **TIP:** 3 capsules of blinded TIP at 28 mg dosage strength, inhaled o.d. via the T-326 Inhaler, for 112 days (on treatment).
- **TIP/placebo cyclical:** patients will take the same doses, i.e. 3 capsules o.d., by alternating TIP 28-days with placebo 28-days for 2 cycles for a total of 112 days.
- **Placebo:** The reference product consists of placebo capsules (DSPC/CaCl₂). The dose regimen for the reference product is 3 capsules blinded, inhaled o.d. via the T-326 Inhaler, for 112 days (on treatment).

Cohort B: 5 capsules o.d.

- **TIP:** 5 capsules of blinded TIP at 28 mg dosage strength, inhaled o.d. via the T-326 Inhaler, for 112 days (on treatment).
- **TIP/placebo cyclical:** patients will take the same doses, i.e. 5 capsules o.d., by alternating TIP 28-days with placebo 28-days for 2 cycles for a total of 112 days.
- **Placebo:** The reference product consists of placebo capsules. The dose regimen for the reference product is 5 capsules blinded, inhaled o.d. via the T-326 Inhaler, for 112 days (on treatment).

[figure not shown]
Cohort C: 4 capsules b.i.d.

- **TIP:** 4 capsules of blinded TIP at 28 mg dosage strength, inhaled b.i.d. in the morning and in the evening via the T-326 Inhaler, for 112 days of treatment.
- **TIP/placebo cyclical:** patients will take same doses, i.e. 4 capsules b.i.d., by alternating TIP 28-days with placebo 28-days for 2 cycles for a total of 112 days.
- **Placebo:** The reference product consists of placebo capsules. The dose regimen for the reference product is 4 capsules blinded, inhaled b.i.d. via the T-326 Inhaler, for 112 days (on treatment).

There will be 3 study epochs with a total of 9 visits ([Figure 1](#)):

- Screening: up to 28 days with 1 clinic visit
- Double-blind treatment (within cohort): 112 days with 6 clinic visits [Visit 101 (Day 1), Visit 102 (Day 8), Visit 103 (Day 29), Visit 104 (Day 57), Visit 105 (Day 85) and Visit 106 or study treatment discontinuation (TD) (Day 113)]
- Follow-up: 56 days with 2 clinic visits [Follow-up Visit 201 (Day 141) and Follow-up Visit 202 or premature subject/patient discontinuation (PSD) (Day 169)]

The total duration of the study is expected to be up to 196 days. Patients will be assessed for safety, tolerability and efficacy (see protocol [[Table 6-1 – Assessment schedule](#)]).

Figure 1 Study design

The primary efficacy endpoint is the absolute change from baseline to Day 29 of treatment in the bacterial load in sputum in log₁₀ colony forming units (CFUs) of *P. aeruginosa*. Baseline is defined as the last measurement prior to the first dose of blinded study drug.

No interim analysis for efficacy is planned. There is an independent data monitoring committee (DMC) assigned to monitor the safety during the study; further details are defined in the DMC Charter.

1.2 Study objectives and endpoints

1.2.1 Primary objectives

- To evaluate the effect of different doses of TIP, administered o.d. or b.i.d., on the change in *P. aeruginosa* bacterial load in sputum as assessed by the change in CFUs from baseline to Day 29 of treatment, each compared to placebo.
- To assess the safety and tolerability with different doses of TIP, administered o.d. or b.i.d., and different regimens (TIP and TIP/placebo cyclical) during the treatment epoch (112 days) and during the follow-up epoch (56 days), each compared to placebo.

1.2.2 Secondary objectives

- To assess the effect of different doses of TIP administered o.d. and one b.i.d. dose and different regimens (TIP and TIP/placebo cyclical) on the frequency, rate (by patient months), severity and time to onset of pulmonary exacerbations at the end of the treatment epoch and over the entire study, each compared to placebo.
- To assess the efficacy profile of different doses of TIP administered o.d. and one b.i.d. dose and different regimens (TIP and TIP/placebo cyclical), as measured by the time to first use, proportion of patients requiring anti-pseudomonal antibiotics (overall, oral, parenteral) and the duration of treatment, each compared to placebo.

[figure not shown]
- To assess the time to first hospitalization, proportion of patients requiring hospitalization and the duration of hospitalization due to serious respiratory-related AEs (other than those regularly scheduled hospitalization that were planned prior to study start).
- To assess the pharmacokinetic concentrations of tobramycin in serum and in sputum from different doses of TIP administered o.d. and one b.i.d. dose and different regimens (TIP and TIP/placebo cyclical).
- To assess the antimicrobial efficacy of TIP over the entire study duration, as measured by the absolute change in *P. aeruginosa* -CFUs in sputum from baseline to each post-baseline treatment visit and during the follow-up visits.
- To evaluate the safety profile of TIP in terms of clinical laboratory results.
- To evaluate the safety profile of TIP in terms of audiology findings throughout the treatment epoch (subgroup of all patients that are in enrolled at sites that are adequately equipped and trained to perform audiologic assessments).
- To evaluate the safety profile of TIP in terms of acute change in forced expiratory volume at 1 second (FEV₁) % predicted values from pre-dose to 30±15 minutes after completion of study drug administration at the clinical site at visits during the treatment epoch.
- To evaluate the impact of treatment with TIP on the Respiratory Symptom Scale Quality of Life Questionnaire for Bronchiectasis (QOL-B) by measuring change from baseline to all post-baseline visits.

[figure not shown]
Table 1-1 Primary and secondary objectives and related endpoints

Objective	Endpoint	Statistical Analysis
Primary		
To evaluate the effect of different doses of TIP on the change in P. aeruginosa bacterial load in sputum at Day 29	Change from baseline to Day 29 in P. aeruginosa density in sputum (log ₁₀ CFUs)	Section # 2.5.2
To assess the safety and tolerability with different doses of TIP and different regimens, on treatment epoch and over entire study duration	Safety: incidence rate of AEs/Serious AEs by MedDRA primary SOC and PT terms Tolerability: incidence and severity of local AEs (eg. cough, bronchospasm, dysgeusia, dry mouth, etc.)	2.7.1
Secondary		
To assess the antimicrobial efficacy of TIP over the entire study duration	Change from baseline to each post-baseline visit in P. aeruginosa density in sputum (log ₁₀ CFUs)	2.6.3.1
To assess the effect of different doses of TIP and different regimens on pulmonary exacerbation at the end of treatment epoch (Day 113) and over the study period	Time to first pulmonary exacerbation by exacerbation category Duration of pulmonary exacerbations by exacerbation category Exposure adjusted rate of exacerbations Proportion of patients with at least one pulmonary exacerbation by exacerbation category Proportion of patients who permanently discontinued study drug due to pulmonary	2.6.3.2

[figure not shown]
Objective	Endpoint	Statistical Analysis
To assess the efficacy profile of different doses of TIP and different regimens as measured by anti-pseudomonal antibiotics usage during the treatment epoch (through Day 113) and the study period	exacerbation Time to permanent study drug discontinuation due to pulmonary exacerbation Time to first use (overall, oral, and -parenteral) of anti-pseudomonal antibiotics usage	2.6.3.3
To assess the hospitalization (other than those regularly scheduled hospitalization that were planned prior to study start)	Proportion of patients used anti-pseudomonal antibiotics usage Duration of anti-pseudomonal antibiotics usage Time to first hospitalization due to serious respiratory-related AEs Number of hospitalizations due to serious respiratory-related AEs Proportion of patients requiring hospitalization due to serious respiratory-related AEs	2.6.3.4
To evaluate the safety profile of TIP in terms of clinical laboratory results	Duration of hospitalization due to serious respiratory-related AEs Laboratory results (hematology, serum chemistry, urine dipstick tests): means, mean changes from baseline, frequency/shift tables by visit	2.7.3
To evaluate the audiology safety profile of TIP	Audiology findings (selected centers) by visit	2.7.4.1
To evaluate the safety profile of TIP in terms of bronchial hyperreactivity	visit Acute change in FEV ₁ % predicted values from pre-dose to 30±15 minutes after completion of study drug administration at the clinical site at visits during the treatment epoch	2.7.4.4
To evaluate the treatment effect of TIP on the Respiratory Symptom Scale Quality of Life Questionnaire for Bronchiectasis (QOL-B)	Change from baseline to all post-baseline visits	2.10
Pharmacokinetic concentrations of tobramycin in serum and in sputum	Concentration data at scheduled visits and timepoints	2.8

1.2.3 Exploratory objectives

- To explore the characteristics of the post-inhalational events at all visits during the treatment epoch.

[figure not shown]
[figure not shown]
[figure not shown]

[figure not shown]
[figure not shown]
[figure not shown]

- To explore the impact of healthcare resource utilization of TIP treatment.

Table 1-2 Exploratory objectives and related endpoints

Objective	Endpoint	Statistical Analysis

Objective	Endpoint	Statistical Analysis
		
To explore the characteristics of the post-inhalational events	Separate summaries for post-inhalation clinical events and post-inhalation adverse events: Proportion of patients experiencing events at each visit Proportion of patients experiencing events that are ongoing at the completion of the visit Proportion of patients experiencing events with an action taken to reduce the event Time of onset of event Duration of event Number of post-inhalation events Event rate adjusted for exposure	2.7.4.3
		
To explore the impact of healthcare resource utilization of TIP treatment	All scheduled and unscheduled visits	2.7.4.5
		

2 Statistical methods

The study is characterized by 3 cohorts (corresponding to 3 doses). Each cohort consists of TIP, TIP/placebo cyclical, or placebo in a ratio of 2:2:1. Data will be summarized and analyzed by cohort/dose, treatment arms (including combined treatments) and/or pooled by continuous, cyclic and placebo as appropriate. For the efficacy analyses, the placebo patients will be pooled from the 3 cohorts.

2.1 General information

██. Statistical analyses will be performed using SAS® Version 9.3 (or higher).

In general, all data will be reported as observed. No imputation will be performed for the primary efficacy analysis. Supportive and sensitivity analyses are discussed in [Section 2.5.4](#) to evaluate the robustness of primary analysis results.

Descriptive statistics (n, mean, standard deviation [SD], median, minimum, and maximum) will be calculated for continuous data. Minimum and maximum will be presented to the same number of decimal places as reported/collected, 1 additional decimal place for mean and median, and 2 additional decimal places for SD. Derived data will be reported to 1 additional decimal place as the reported data.

Categorical data will be summarized using n and percentages based on the number of non-missing values. Percentages will be presented to 1 decimal place. The number of missing values will be presented as a separate category with no percentage, but only if 1 or more patients are missing data for the summary. Otherwise, all categories will be presented (even if no patients are counted in the category). Counts of zero in any category will be presented without a percentage.

2.1.1 General definitions

Study drug is defined as any single dose of TIP or placebo administered to the patient as part of the required study procedures.

The date of first dose of study drug is defined as the date of first administration of TIP or placebo; the date of last dose of study drug is defined as the date of the last administration of TIP or placebo.

For dates on or after the date of first dose of study drug, study day is defined as [date of interest – date of first dose of study drug] + 1. For dates before the date of first dose of study drug, study day is defined as [date of first study drug – date of interest].

For each visit, the date recorded by the investigators in the eCRF (variable SVSTDTC in the SDTM SV dataset) will be considered as the visit date in all the algorithms and the listings.

In general, the nominal visits will be used for the by visits summaries. However, for early treatment discontinued patients, data collected at end of treatment (EOT) visit will be mapped to next planned visits after their last scheduled visits before the discontinuation.

Baseline is defined as the last non-missing result prior to the first administration of study drug.

End/last date of study for each patient is defined by the date of last contact as recorded in the database.

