6.2 Patient demographics/other baseline characteristics

Patient demographic and baseline characteristic data to be collected on all patients include: date of birth, age, sex, race, ethnicity, and source of patient referral. Relevant medical history or current medical condition data include data present before signing informed consent. Where possible, diagnoses and not symptoms will be recorded. History of pulmonary exacerbations will be collected on a specific medical history CRF.

A standard 12 lead ECG will be performed at screening (Visit 1). For eligibility in the study the interpretation of the tracing must be made by a qualified physician and documented. The original ECGs, appropriately signed, should be collected and archived at the study site.

ECGs must be recorded after 10 minutes rest in the supine position to ensure a stable baseline. The preferred sequence of cardiovascular data collection is ECG collection first, followed by vital signs, blood sampling, and spirometry. The Fridericia QT correction formula (QTcF) should be used for clinical decisions.

Each ECG tracing should be labeled with study number, subject initials, subject number, date and time, and filed in the study site source documents. For any ECGs with subject safety concerns, two additional ECGs should be performed to confirm the safety finding. If the ECG findings are clinically relevant and would prevent the patient from participating in the study (taking into account the overall status of the patient as well as the medication profile), the patient should be recorded as a screen failure, should NOT be randomized and should not receive treatment.

Clinically significant abnormalities should be recorded on the relevant section of the medical history/Current medical conditions/AE CRF page as appropriate.

Investigators will have the discretion to record abnormal test findings on the medical history CRF whenever in their judgment, the test abnormality occurred prior to the informed consent signature.

Conditions associated with bronchiectasis disease and signs or symptoms including etiology and age at diagnostic will be captured by using a specific BE-related Medical History CRF page.

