2.1.3 Listings

All data collected in the eCRF and diaries will be presented in the listings.

Data will be presented in listings in the order of cohort [Cohort A: 3 capsules OD, Cohort B: 5 capsules OD and Cohort C: 4 capsules BID], treatment arm [TIP, TIP/Placebo Cyclical and Placebo], site/patient identifier, assessment date and assessment (in order collected in the eCRF, unless specified otherwise). AE listings will include the AE start day and AE stop day relative to the first day of study drug. Dates will be presented in format DDMMYYYY.

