2.3 Patient disposition, demographics and other baseline characteristics

The number of patients screened and the number of screen failures will be presented (overall).

The number of patients included in each of the Randomized, SAF, FAS, PPS, AUD, PKAS and PKSSAS populations will be summarized for each cohort, treatment arm and overall.

Patients who complete the treatment phase and patients who complete the follow-up phase will be summarized using the FAS. Patients who discontinue from the treatment phase and patients who discontinue the follow-up phase will be summarized overall and by reason for discontinuation using the FAS.

The FAS will be used to summarize the following by cohort and treatment arm:

- Demography: age, age group (< 65 years and >=65 years), gender, race and ethnicity, weight (kg), height (cm), body mass index (BMI).
- Baseline characteristics: baseline spirometry (FEV₁, [REDACTED]) %predicted values, MIC, macrolide use, bronchodilators, inhaled corticosteroids, tobramycin MIC=>8 at baseline, BSI.
- Medical history - ototoxicity
- History of pulmonary exacerbations
- Bronchiectasis-related medical history
- Spirometry assessed at screening
- Previous hospital admissions and exacerbations
- Other relevant medical history

Age will be calculated as the difference between year of birth and year of informed consent.

The following table will be used to derive the BSI:

Table 2-1 Severity criteria for BSI

Criteria/Point	0	1	2	3	4	5	6
Age	<50		50-69		70-79		80+
BMI (kg/m ²)	≥18.5		<18.5				
FEV ₁ % predicted	>80%	50-80%	30-49%	<30%			
Hospital admissions in the past 2 years	No					Yes	
Exacerbation frequency in the last 12 months	0-2		≥3				
MRC dyspnoea	1-3		4	5			
Colonisation status	Not colonised	Chronic colonisation		P.aeruginosa colonisation			
Radiological severity	<3 lobes involved	≥3 lobes or cystic changes					

Medical history recorded in the eCRFs will be reviewed to determine whether a patient had a hospital admission in the past 2 years. The pulmonary exacerbation history eCRF data will be reviewed to determine the exacerbation frequency in the 12 months prior to Screening.

If any individual severity criteria cannot be assessed for a patient due to missing or incomplete data, the BSI total score will not be derived.

Smoking history will be listed in patient listing only.

Listings will be provided to show all demographic and baseline characteristics using the randomized population.

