5.1.4 Relative day of AE onset and AE end imputations

The relative day of AE onset will be calculated as follows:

- AE start date - date of first dose of study drug (if AE start date is completely known)
- missing (if AE onset date is incomplete or unknown)

The relative day of AE end will be calculated as follows:

- AE end date – date of first dose of study drug (if AE end date is completely known)
- missing (if AE end date is incomplete or unknown)

The duration of an AE will be calculated as follows:

- AE end date – AE start date + 1 (when both dates are completely known)

- Date of end of study completion/discontinuation – AE start date + 1 (when the AE onset date is fully known but the AE is not resolved at the end of the trial): in this case the duration will be presented as “>x days” in the listing rather than “x days”
- missing (when the AE start date is incomplete or unknown, or when the AE has resolved but with an incomplete or unknown end date, or when the AE onset date is > date of end of completion/discontinuation and the AE is not resolved)

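### Minor: the SAP's pre-dose study day has its subtraction reversed, its AE day conflicts with its study day, and its year-difference age is too high for any patient whose birthday falls after consent

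*SAP*

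**What the plan says.** **Study day.** For dates from first dose onward, SAP 2.1.1 gives: "study day is defined as [date of interest – date of first dose of study drug] + 1". For earlier dates it gives: "For dates before the date of first dose of study drug, study day is defined as [date of first study drug – date of interest".

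**AE day.** SAP 5.1.4 has its own rule for onset, "AE start date - date of first dose of study drug (if AE start date is completely known", and for end, "AE end date – date of first dose of study drug (if AE end date is completely known". Neither adds 1. SAP 2.1.3 puts these numbers in front of the reader: "AE listings will include the AE start day and AE stop day relative to the first day of study drug".

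**Age.** SAP 2.3: "Age will be calculated as the difference between year of birth and year of informed consent". Protocol 6.2 lists among the data collected on all patients: "date of birth, age, sex, race, ethnicity, and source of patient referral". Age is summarized, split at 65 years, and scored in the BSI (SAP Table 2-1), where the points step up by 2 at ages 50, 70 and 80.

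**The concern.** These are programming specifications, so a programmer will either implement them literally or depart from the SAP without saying so.

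Under the pre-dose rule, one study-day number can stand for two different dates, one in screening and one on treatment. The missing +1 means the same calendar date carries different day numbers under two sections of one document. This is also out of step with the SAP's inclusive counting elsewhere: treatment duration (2.4.1) and AE duration (in 5.1.4 itself) both add 1. In the cyclical arms Day 29 is the first day of the placebo period, so an AE starting that day but listed as 28 could be taken for one on the last active day by a reader who does not know the convention.

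The age rule errs in one direction only. It pushes some patients over the 65-year cut and the BSI age cuts too early.

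**Working it through.** **1. Study day.** Let k be the number of days from first dose, negative before it. SAP 2.1.1 gives k + 1 for k ≥ 0, and -k for k < 0.

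| Days from first dose | Study day (2.1.1) | AE day (5.1.4) | Study day minus AE day |
|---|---|---|---|
| -28 | 28 | -28 | 56 |
| -8 | 8 | -8 | 16 |
| -7 | 7 | -7 | 14 |
| -1 | 1 | -1 | 2 |
| 0 | 1 | 0 | 1 |
| 7 (Visit 102) | 8 | 7 | 1 |
| 28 (Visit 103) | 29 | 28 | 1 |
| 112 (Visit 106) | 113 | 112 | 1 |

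The rule for dates from first dose onward reproduces every visit label in the plan: 1, 8, 29, 57, 85, 113, 141 and 169. The pre-dose rule does not reproduce the one pre-dose label that the documents give. Table 6-1 has -28 to -7; the formula returns +28 to +7. A date k days before first dose shares its number with the date k - 1 days after it, so the eighth day before dosing has the same number as Visit 102. Reversing the subtraction returns -28 to -7.

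**2. AE day.** On or after first dose, study day minus AE day is (k + 1) - k = 1, always. For an AE k days before first dose the two rules give +k and -k, which is a change of sign and a gap of 2k. Section 5.1.4 has the right sign there.

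**3. Age.** The year difference equals completed age if the birthday has passed by the consent date, and completed age + 1 if it has not. It is never too low. For example, someone born in November 1953 who consents in March 2018 gets 2018 - 1953 = 65, but is 64.

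The documents give neither birth dates nor consent dates, so the share affected has to be assumed. With birthdays uniform over the year:
- consent spread evenly over a full year: 49.9%;
- consent uniform from an assumed start to 2 October 2018, when recruitment stopped (SAP 1): 47% (start July 2017) to 62% (start January 2018), for starts between January 2016 and February 2018;
- a single consent date: nearly 100% on 1 January, 0% on 31 December.

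At one half, 107 × 0.5 = 53.5 of the 107 randomized patients would be shown one year too old.

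A group changes only for patients whose completed age is 64 (the 65-year split), or 49, 69 or 79 (BSI), and whose birthday falls after consent. I took ages as normal, truncated below at 18 (the entry limit), with mean 55 to 68 and SD 10 to 15, and consent dates uniform over the year:
- BSI age points wrong: 2.4% to 3.4%, so 107 × 0.024 = 2.6 to 107 × 0.034 = 3.6 patients;
- 65-year group wrong: 1.1% to 2.0%, so 107 × 0.011 = 1.2 to 107 × 0.020 = 2.1 patients.

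At mean 64 and SD 12 the figures are 3.0% and 1.7%. If the overstated share were 62% rather than one half, these percentages would be about a quarter higher (0.62 / 0.50 = 1.24).

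**The case against.** The best reply is that nothing inferential depends on these rules. By-visit summaries use nominal visits (SAP 2.1.1), treatment-emergent status is set by dates (2.7.1), exposure and AE duration are computed from dates, and neither age nor BSI enters the primary ANCOVA (2.5.2) or the Cox and negative binomial models (2.6.3). The only subgroup named in 2.2.1 is macrolide use. The SAP already calls its inferential analyses exploratory after early closure. All of this stands, and it limits the point to listings and descriptive tables.

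It also stands that 5.1.4 defines a separately named quantity. An elapsed-day count is not an error in itself; the fault is that two sections number the same date differently. A year difference is likewise a stated convention, but a needlessly biased one when the full birth date is collected.

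Two stronger readings are tempting and should be resisted:
- A reader might infer from 2.1.1 that screening AEs would appear to have occurred around Visits 102 and 103. They would not. AE days follow 5.1.4, which makes an AE 10 days before dosing -10.
- A reader might infer that listed AE days cannot be matched to the Day 29 and Day 113 visits. They can, because the shift is a constant one day from first dose onward.

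**Conclusion.** The point holds as a minor one, wrong as written. The reversed subtraction and the missing +1 follow from the text with no assumption. The first affects every pre-dose study day derived by 2.1.1, but not AE days. The second affects every AE with a complete date on or after first dose, by exactly one day. That age is overstated, and never understated, also follows from the text. How many patients are affected does not: about half (47% to 62%) rests on uniform birthdays and assumed recruitment dates, and the 1 to 4 of 107 misplaced patients rest on an assumed age distribution. The text available for review gives no ground for saying that treatment-emergent status, a by-visit summary or an efficacy result would change.

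**What to change.** - **SAP 2.1.1:** for dates before first dose, set study day to date of interest minus date of first dose (negative, with no Day 0).
- **SAP 5.1.4:** replace the two relative-day formulas with the 2.1.1 rule as corrected, so that an AE on the first-dose date is Day 1 in both sections.
- **SAP 2.3:** define age as completed years from date of birth to date of informed consent, keeping the year difference only where the full birth date is unavailable. This fallback also covers any place where privacy rules limit the data to year of birth.

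The cost is three lines of SAP text and the matching derivation code. No design feature, data collection or clinical rule changes.
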